## 4. DATA CONVENTIONS AND VISIT WINDOWS

### 4.1. Data Conventions

#### 4.1.1. Missing Data and Outliers

Every effort will be made to obtain required data at each scheduled evaluation from all subjects who have been randomized. In situations where it is not possible to obtain all data, it may be necessary to impute missing data. These situations are described below. Unless otherwise specified, all other missing data will not be imputed.

##### 4.1.1.1. Missing Severity or Relationship for Adverse Events

Adverse events (AEs) with missing severity (Common Terminology Criteria for Adverse Events [CTCAE] toxicity grade) will have the severity imputed as 'Grade 3' or 'Severe'. Adverse events with missing relationship to IMP will have the relationship imputed as 'Related' if the AE started after the first dose of IMP. Actual values will be presented in the data listings.

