### 3.4.6. Adverse Events (AEs)

An AE is defined as any untoward medical occurrence in a patient or clinical trial subject, temporally associated with the use of trial intervention, whether considered related to the trial intervention.

All adverse events will be recorded on the ADVERSE EVENTS CRF. Adverse events with missing severity will have the severity imputed as 'Grade 3' for the AE tabulations. Adverse events with missing relationship to IMP will have the relationship imputed as 'Related' for the AE tabulations if the AE started on or after the first dose of IMP. However, in the data listings these missing intensity and/or relationship will be presented as missing.

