##### 4.1.1.2. Incomplete or Missing Dates

An incomplete date occurs when the exact date an event occurred or ended cannot be obtained from a subject. The database contains data fields for month, day, and year. A date is incomplete if at least one of these three fields is not known.

For many of the planned analyses, a complete date is necessary to determine if the event should be included in the analysis (ie, if the event is treatment-emergent) or to establish the duration of an event. In such cases, incomplete dates will be imputed.

For the purposes of handling partially reported start and stop dates for an event the following algorithm will be applied:

- Missing start day, but month and year present:
  - If the event occurs same month and year as the dosing of IMP, then the start day of the IMP will be assigned to the day of first dose of IMP.
  - Otherwise, the start day will be set to the first day of the month.
- Missing start day and month, but year present:
  - If event occurs in the same year as IMP dosing, then the start date of the event will be assigned to Day 1.
  - Otherwise, the start day and month will be set to 01 January.
- Missing all components of a start date:
  - Assign the date of Day 1.
- Missing end day, but month and year present:
  - The day will be set to the last day of the month.
- Missing end day and month, but year present:

- The end day and month will be set to the date of study completion/discontinuation.
- However, if study completion/discontinuation year is greater than the year of the event, then the day and month will be set to 31 December.
- In the event of a completely missing end date (year not present and ongoing not checked), the end date will be considered as ‘ongoing’ and will not be imputed.

If any imputed date causes the end date to occur prior to the start date of the event, the start date of the event will be used for the imputation of the end date. If any imputed date causes the start date of the event to occur after the end date of the event, the end date of the event will be used for the imputation of the start date. If the imputed date is later than the date of study withdrawal, then the date of study withdrawal will be imputed for the date. In subject data listings, start and stop date of events will be displayed as reported on the eCRF (ie, imputed values will not be listed).

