#### 4.1.1.3. Missing Time

If time is missing for a laboratory assessment taken on the first day of IMP administration, ie Day 1, but the time of IMP administration is available, then time for the laboratory assessment will be assumed to have occurred prior to IMP administration and will serve as the baseline value, assuming that the timepoint for the assessment was designated as predose. If the timepoint for the assessment was designated as postdose, then the assessment will be assumed to have been taken postdose.

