### **Treatment-emergent Adverse Event (TEAE)**

Any event reported on the eCRF that occurs on or after the initiation of IMP and up to the final follow-up contact is considered treatment-emergent. Additionally, it is assumed that an Adverse Event which was reported to have started on Day 1 without an associated onset time may have occurred after the initiation of IMP. Hence, Adverse Events occurring on Day 1 with no associated onset time are assumed to be treatment-emergent.

For Part A, treatment-emergent adverse events will be attributed to a period based on the start date. An adverse event starting on or after the initiation of IMP in Period 1 and before dosing with IMP for Period 2, or through follow-up contact if subject discontinues prior to Period 2, is considered a Period 1 TEAE. For Cohort 1 and 2, an adverse event starting on or after the initiation of IMP in Period 2 and before dosing with IMP for Period 3, or through follow-up contact if subject discontinues prior to Period 3 is considered a Period 2 TEAE. An adverse event starting on or after the initiation of IMP in Period 3 and before dosing with IMP for Period 4, or through follow-up contact if subject discontinues prior to Period 4, is considered a Period 3

TEAE. An adverse event occurring after dosing for Period 4, through follow-up contact, is considered a Period 4 TEAE.

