### **Treatment-emergent Laboratory Toxicity**

A treatment-emergent laboratory toxicity is defined as an increase of at least one toxicity grade from the baseline assessment at any post baseline visit. The post baseline visit must occur after the administration of IMP and through the follow-up contact. For defining treatment-emergent laboratory events, it is assumed that a laboratory assessment obtained on Day 1 with missing collection times occurred prior to the initiation of IMP unless a protocol deviation is identified. If the relevant baseline assessments are missing, then any graded toxicity (ie, at least Grade 1) is considered treatment-emergent.

For Part A, treatment-emergent laboratory toxicities will be attributed to a period based on the start date. A laboratory toxicity occurring on or after the initiation of IMP in Period 1 and before dosing with IMP for Period 2, or through the follow-up contact if subject discontinues prior to Period 2, is considered a Period 1 treatment-emergent toxicity. For Cohort 1 and 2, a laboratory toxicity occurring after dosing for Period 2 and before dosing with IMP for Period 3, or through the follow-up contact if subject discontinues prior to Period 3, is considered a Period 2 treatment-emergent toxicity. A laboratory toxicity occurring on or after the initiation of IMP in Period 3 and before dosing with IMP for Period 4, or through the follow-up contact if subject discontinues prior to Period 4, is considered a Period 3 laboratory toxicity. A laboratory toxicity occurring after dosing for Period 4 through the follow-up contact post Period 4 is considered a Period 4 treatment-emergent toxicity.

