### 5.9.1. Adverse Events

Adverse events will be mapped to a Medical Dictionary for Regulatory Activities (MedDRA) version 25.1 or later by system organ class, preferred term, and severity. If a subject experiences multiple events that map to a single preferred term, the greatest Common Terminology Criteria for Adverse Events (CTCAE) toxicity grade and strongest investigator assessment of relation to IMP will be assigned to the preferred term for the appropriate summaries. Events with missing severity or relationship, will be classified as outlined in [Section 4.1.1.1](#).

For Part A, all TEAEs will be attributed to a treatment period based on start date as specified in [Section 4.2.1](#). Any TEAE occurring during the washout period will be attributed to the treatment most recently administered.

The occurrence of TEAEs will be summarized by treatment group for Part A and Part B, using preferred terms, system organ class, and severity. Separate summaries of TEAEs, treatment-emergent serious adverse events (TESAEs), TEAEs by severity, TEAEs related to IMP, AESIs, and events leading to the discontinuation of study will be generated by system organ class and preferred terms. For Part B, a separate analysis of AEs leading to the discontinuation of IMP will be provided.

All AEs reported will be listed for individual subjects showing both verbatim and preferred terms and treatment group at onset of the AE. All AEs that occurred prior to the initiation of IMP will be excluded from the tables but will be included in the listings.

Missing onset dates will be imputed as previously outlined in [Section 4.1.1.2](#) as required to determine treatment-emergent events.

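### The SAP gives conflicting rules for two rare Day 1 records: an AE with no causality and no onset time, and a postdose lab sample with no collection time

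*SAP*

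**What the plan says.** **AE causality.** SAP 3.4.6 imputes a missing relationship as Related "for the AE tabulations if the AE started on or after the first dose of IMP". SAP 4.1.1.1 makes the same imputation "if the AE started after the first dose of IMP". The analysis section, SAP 5.9.1, settles which one feeds the tables: "Events with missing severity or relationship, will be classified as outlined in" Section 4.1.1.1.

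Two other rules place events on the first dosing day. The TEAE definition in SAP 4.1.2 says "Adverse Events occurring on Day 1 with no associated onset time are assumed to be treatment-emergent". For a start date with every component missing, SAP 4.1.1.2 says "Assign the date of Day 1"; some partly missing dates also move to Day 1 or to the day of first dose.

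**Laboratory time.** SAP 4.1.1.3 covers a sample from the first dosing day with no time recorded, where the dosing time is known. It follows the designated timepoint. A predose designation makes the sample predose and baseline. For the other case: "If the timepoint for the assessment was designated as postdose, then the assessment will be assumed to have been taken postdose". The treatment-emergent laboratory toxicity definition in SAP 4.1.2 instead assumes that "a laboratory assessment obtained on Day 1 with missing collection times occurred prior to the initiation of IMP unless a protocol deviation is identified". It does not mention the designated timepoint.

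**The concern.** Each pair of rules can put the same record in opposite classes, and the SAP does not say which rule prevails. TEAEs and clinically significant laboratory changes are primary endpoints in both parts, and protocol 9.4.2 commits to AE summaries by relationship to IMP.

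In each pair, one reading is less cautious about the day of first dosing: a related event may go uncounted in one table, or a postdose laboratory value may be treated as predose. If such a record turns up, the choice of rule would be made after it has been seen.

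**Working it through.** The plan gives no figure to reproduce, so the check is to trace each record through the rules.

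**Record 1: an AE dated Day 1 with no onset time and no causality**

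1. It is treatment-emergent under the TEAE definition. An AE whose start date was imputed to Day 1 under 4.1.1.2 sits on the same date.
2. Under 3.4.6, Day 1 satisfies *on or after*, so the relationship becomes Related.
3. Under 4.1.1.1 the condition is *after*. With no clock time, a program has only dates to compare, and Day 1 is not later than Day 1. The condition fails.
4. SAP 4.1.1 leaves missing data unimputed unless a rule says otherwise, so the relationship stays missing.
5. Result: on the date comparison the event is in the related-TEAE table under 3.4.6 and absent from it under 4.1.1.1. It is in the all-TEAE and severity tables and in the listings under both.
6. In Part A the conflict arises only at a participant's first dose. Events in later periods are after the first dose on either wording.

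**Record 2: a Day 1 sample designated postdose, no time, no protocol deviation identified**

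| Rule | Class | Consequence |
|---|---|---|
| SAP 4.1.1.3 | Postdose | Can count as a post-baseline value |
| Laboratory-toxicity definition | Predose | Cannot count as treatment-emergent toxicity |

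The separate laboratory-abnormality definition has no missing-time rule, so 4.1.1.3 would govern there. One sample could therefore be a treatment-emergent abnormality in one output and a predose value in another.

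The effect on baseline differs by part:

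- Part A, Cohorts 1 and 2: SAP 4.2.1 uses the Day -1 check-in sample as the period baseline for safety laboratory tests not done predose on Day 1. The schedule has no predose Day 1 safety sample, so baseline is protected.
- Part B: baseline is the last value before IMP, and 4.2.1 does not apply. A sample reclassified as predose could be taken as that value.

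**How often**

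- Protocol 10.3.3 obliges the investigator to assess causality for every AE.
- SAP Appendix 9.1 schedules safety laboratory samples in Part A at screening, check-in, 24 h and 48 h. In Part B they are at screening and on Days -1, 4, 7, 10, 14 and 17. None falls on Day 1, so only an unscheduled or repeat sample could be affected.

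**Weight of one record**

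- SAD: 8 participants at 3:1 gives 8 × 3/4 = 6 active per dose; 1/6 = 16.7%.
- MAD: 8 active per dose; 1/8 = 12.5%.

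These are the weights of any single participant in cohorts of this size. They are not an expected error.

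**The case against.** **On AEs.** A dose happens at a time, and 4.1.1.1 does not say that *after* means a later calendar date. An AE two hours after dosing on Day 1 started after the dose. For an AE with no onset time, the TEAE definition reasons that it may have begun after dosing. If that assumption is carried into 4.1.1.1, the event is imputed Related, as under 3.4.6. Protocol 8.4.1 also records AEs only from the first dose, so a recorded AE is almost always at or after dosing. This stands: the two sections can be reconciled. What remains is that 4.1.1.1 does not refer to that assumption, and a date comparison gives the other answer.

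**On laboratory samples.** The conflict needs a Day 1 sample designated postdose. None is scheduled, and nothing in the SAP gives an unscheduled sample a designation; without one, 4.1.1.3 does not call it postdose and the rules do not collide. The toxicity definition also excepts identified protocol deviations. This narrows the case greatly. It does not reach a sample that is designated postdose, lacks only its time and has no deviation identified.

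**A stronger reading.** A reader might infer that the SAP hides first-dose effects, or that an untimed Day 1 sample becomes the baseline throughout the trial. The documents do not support either. The AE stays in the all-TEAE tables, and the listings show its causality as missing. For the SAD cohorts, 4.2.1 fixes the laboratory baseline at check-in. The toxicity definition makes its assumption for defining treatment-emergent events and does not itself assign a baseline, so even in Part B a changed baseline is only possible.

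**Conclusion.** Both inconsistencies are in the current SAP text, and their reach is small.

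The AE conflict changes a result only if causality is missing, onset falls on the first dosing day with no time (or was imputed to that day), and the program compares dates. The laboratory conflict changes a result only for a Day 1 sample that is designated postdose and untimed, with no identified deviation. On the protocol's own requirements and schedule, few or no such records should arise.

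The laboratory conflict is the firmer of the two. As written, the toxicity definition misclassifies a sample labelled postdose, whereas the AE wording can be read consistently. No hypothesis test, sample size or dosing rule is affected. This is a low-priority correction, worth making because it costs almost nothing and removes a choice before the data are seen.

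**What to change.** Make two wording edits in the SAP:

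1. In 4.1.1.1, adopt the condition from 3.4.6 ("if the AE started on or after the first dose of IMP") and add that it includes Day 1 events with no onset time. This matches the TEAE definition.
2. In the treatment-emergent laboratory toxicity definition, replace the missing-time assumption for Day 1 with a reference to 4.1.1.3, so that a sample designated postdose is never treated as predose.

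The cost is two sentences of text and a check that the AE and laboratory programs follow them. No data collection changes.

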##### 4.1.1.2. Incomplete or Missing Dates

An incomplete date occurs when the exact date an event occurred or ended cannot be obtained from a subject. The database contains data fields for month, day, and year. A date is incomplete if at least one of these three fields is not known.

For many of the planned analyses, a complete date is necessary to determine if the event should be included in the analysis (ie, if the event is treatment-emergent) or to establish the duration of an event. In such cases, incomplete dates will be imputed.

For the purposes of handling partially reported start and stop dates for an event the following algorithm will be applied:

- Missing start day, but month and year present:
  - If the event occurs same month and year as the dosing of IMP, then the start day of the IMP will be assigned to the day of first dose of IMP.
  - Otherwise, the start day will be set to the first day of the month.
- Missing start day and month, but year present:
  - If event occurs in the same year as IMP dosing, then the start date of the event will be assigned to Day 1.
  - Otherwise, the start day and month will be set to 01 January.
- Missing all components of a start date:
  - Assign the date of Day 1.
- Missing end day, but month and year present:
  - The day will be set to the last day of the month.
- Missing end day and month, but year present:

- The end day and month will be set to the date of study completion/discontinuation.
- However, if study completion/discontinuation year is greater than the year of the event, then the day and month will be set to 31 December.
- In the event of a completely missing end date (year not present and ongoing not checked), the end date will be considered as ‘ongoing’ and will not be imputed.

If any imputed date causes the end date to occur prior to the start date of the event, the start date of the event will be used for the imputation of the end date. If any imputed date causes the start date of the event to occur after the end date of the event, the end date of the event will be used for the imputation of the start date. If the imputed date is later than the date of study withdrawal, then the date of study withdrawal will be imputed for the date. In subject data listings, start and stop date of events will be displayed as reported on the eCRF (ie, imputed values will not be listed).

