##### **Day 1 (Baseline) (Part B)**

Baseline for Part B (Day 1) is defined as the day IMP is first initiated.

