##### **Period Day (Part A)**

For Part A, within each period, Period Day is defined relative to the first day of the sentinel dosing within each phase. Thus, the period day of an event is calculated as:

Period Day = event date – first date of period dosing (+1, if event date  $\geq$  date of Period Day 1)

This calculation will result in negative period days being assigned to visits occurring prior to treatment with IMP within each period, and positive study days being assigned on or after the start of IMP.

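### The SAP's partial-date rule for adverse events, used to place Part A events in a crossover period, can put them under the wrong dose, placebo or food state (minor correction)

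*SAP*

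**What the plan says.** SAP 4.1.1.2 gives a single algorithm, with no qualifier for part or period. Its stated purposes are to decide whether an event is treatment-emergent and to establish its duration.

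- Day missing, month shared with dosing: "then the start day of the IMP will be assigned to the day of first dose of IMP".
- Day missing, any other month: the 1st of that month.
- Day and month missing in the dosing year, or the whole date missing: Day 1.

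Two corrections follow. If the imputed start falls after the end of the event, "the end date of the event will be used for the imputation of the start date". The second begins "If the imputed date is later than the date of study withdrawal" and moves the date back to withdrawal.

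For Part A, SAP 4.1.2.4 says that "treatment-emergent adverse events will be attributed to a period based on the start date". SAP 5.9.1 repeats this, sends missing onset dates to 4.1.1.2 "as required to determine treatment-emergent events", and lists each event with the "treatment group at onset of the AE".

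The reference days differ by place. SAP 4.1.2.4 states "Baseline for Part B (Day 1) is defined as the day IMP is first initiated" for Part B, and for Part A "Period Day is defined relative to the first day of the sentinel dosing within each phase". SAP 4.1.1.3 treats Day 1 generally as the first day of dosing. SAP 4.2.1 uses a Day 1 in every period and speaks of a first dose per analysis period.

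**The concern.** In Part B each participant has one treatment, so an early imputed date leaves the treatment group unchanged. In Part A the period fixes the dose, placebo or food state. A rule designed to err towards calling an event treatment-emergent therefore also decides which treatment the event is counted under, and it does so without using the period, later dose dates or the contact at which the event was recorded.

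Treatment-emergent AEs are a primary endpoint for Part A, and Protocol 9.4.2 plans summaries by dose at onset. A misplaced event blurs the dose-AE relation within a cohort, or the fed versus fasted comparison, in the tables and in the listed treatment at onset. The wording also leaves room for two programmers to place the same event under different doses.

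**Working it through.** The documents give no figure to reproduce, so the check applies the rule to every possible date.

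**Inputs from the documents.** Four single-dose periods with doses at least 5 days apart (SAP 1.1.1). Check-out on Day 3, which is 2 days after dosing (Protocol 4.1.3). Follow-up contact about 14 days after the last dose. Cohort 3 check-out on Day 8, which is Period 2 Day 3 (Protocol Figure 2). The Period 2 dose is therefore on Day 8 − 2 = Day 6, and follow-up on Day 6 + 14 = Day 20, as in Protocol Table 2.

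**Assumptions.** Spacing of 5, 7, 10, 14 or 18 days. The upper end comes from the stated duration of up to 100 days: (100 − 28 screening − 14 follow-up)/3 = 58/3, about 19. Onset is from 3 days after a dose to the day before the next one (Period 4: to day 14), all days equally likely, for 365 first-dose dates. Only the start day is missing. First dose means first in the trial, and the first-dose branch applies only to the month of that dose.

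**Formula.** Under this reading an event k days after a Period 2-4 dose stays in its period only if a 1st of the month falls among the k + 1 days from that dose to onset. There are 12 such days in 365, so

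share moved earlier = 1 − 12 × (mean k + 1)/365.

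- Period 4, k = 3 to 14, mean 8.5: 1 − 12 × 9.5/365 = 0.688 at every spacing.
- Cohort 3, Period 2: the same k range, also 0.688.
- Period 2 or 3: see the table. The pooled column weights periods by their number of onset days; at spacing 5 it is (2 × 2 × 0.852 + 12 × 0.688)/16 = 0.729.

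| Spacing (days) | Mean k, Period 2 or 3 | Moved, Period 2 or 3 | Moved, Periods 2-4 pooled | Moved, all periods |
|---|---|---|---|---|
| 5 | 3.5 | 0.852 | 0.729 | 0.648 |
| 7 | 4.5 | 0.819 | 0.740 | 0.617 |
| 10 | 6 | 0.770 | 0.732 | 0.577 |
| 14 | 8 | 0.704 | 0.698 | 0.528 |
| 18 | 10 | 0.638 | 0.652 | 0.481 |

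Full enumeration (6,570 to 20,805 cases per spacing) gives the same values. No event moves later and no imputed start falls after onset, so neither correction ever acts. If in-clinic onset days are counted too, the Period 2-4 share is 75-80% (spacings 5, 7 and 14) and the Cohort 3 share is 74%.

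**Missing month or whole date.** With Day 1 read as the first dosing day, every such event goes to Period 1.

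**Example.** Doses on 1, 6, 11 and 16 June; onset 20 June, recorded as June. The imputed start is 1 June, so a Period 4 event is counted in Period 1. For the 2 of 8 participants with placebo first, a top-dose event becomes a placebo event.

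**Other readings, all periods.**

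- First period dose within the event's month: 9-53% earlier, 4-26% later.
- Day number of the first dose, applied in any month with a dose: 15-29% earlier, 9-32% later.

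**Direction and size.** For any two periods of Protocol Table 8, two of the four sequences are active in both, one has placebo in the earlier and one in the later. With equal AE rates, moved events split 50% active to another active dose, 25% active to placebo and 25% placebo to active. One moved event changes incidence by up to 1/6 = 17 points at an active dose, 1/8 = 12.5 points in a food state and 1/16 = 6 points in pooled placebo, if the participant has no other event of that term there.

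**The case against.** **The SAP limits the imputation to treatment emergence and duration.** This is partly right, and the wording in 5.9.1 supports it. But on that reading no rule remains for placing a partly dated Part A event in a period.

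**Existing safeguards.** The two corrections act only on dates that are too late. The washout sentence in 5.9.1 sends an event to the most recent treatment, but the date is needed first to know which washout it was. Listings show the date as reported, which helps tracing, but not the imputed date behind the assignment.

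**The contact of first recording adds nothing by itself.** This stands. A reader might infer that it proves the true period. A stop date and a recording contact only limit onset from above, and the current rule already takes the earliest possible date. They leave a single possible period in 28-48% of cases (stop date one day after onset) or 35-52% (contact added), and the current rule is right in all of those. The gain depends on assuming that earlier contacts would have picked the event up. In-clinic stays through Day 3, AE monitoring at later check-ins and continuous domicile in Cohort 3 make that reasonable, but the documents do not show the AE form.

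**Two further inferences go too far.** The imputed date is never late only under the reading worked above. And Day 1 is not meaningless outside Part B, since SAP 4.1.1.3 glosses it generally; it is simply not fixed for the crossover.

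**Scale.** Part A has about 24 closely observed volunteers and a descriptive analysis. That stands, and it sets the weight of the point.

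**Conclusion.** The point holds as a minor correction. Followed as written, the rule can count a Part A event under the wrong dose, placebo or food state. On the first-dose-in-trial reading, with the first-dose branch limited to that dose's month, this happens to about 65-74% of Period 2-4 events and about 69% of Cohort 3 Period 2 events. Those shares are conditional on a missing start day, onset after check-out and the assumed spacings.

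They do not mean that most Part A AEs will be misplaced. The documents give no frequency of partial dates, and few are expected. Safety Review Team decisions are not affected, because the team reviews emerging data before each next dose and does not work from these tables. What remains is a small risk to a primary endpoint's tabulation, with up to 17 points at an active dose for one event, and terms that need defining in any case.

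**What to change.** 1. In SAP 4.1.1.2, correct the quoted sentence so that it sets the start day of the event, and define dosing of IMP, first dose and Day 1 for Part A.
2. Keep the present imputation for treatment emergence and duration, and state that it does not choose the Part A period.
3. For Part A, including Cohort 3, assign a partly dated event to the latest period dosed before the contact at which it was first recorded, provided that this fits the reported month and year and the stop date. State the assumption that events from earlier periods would have been recorded at earlier in-clinic or check-in contacts. Confirm that the AE form or entry date identifies the contact of first recording.
4. Footnote every event assigned this way.

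The cost is a few lines of SAP text and programming. If the assumption holds, the rule recovers the true period in every enumerated case. If it fails, an event that began earlier but was reported late is placed too late; the footnote makes this visible.
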